8. RESEARCH QUESTION AND OBJECTIVES

8.1 RATIONALE FOR PERFORMING THE STUDY

The benefits of tiotropium bromide plus olodaterol FDC have been studied in controlled Phase III trials, however, data regarding quality of life and health status when treated with Spiolto® Respimat® in a real world setting is not available, especially in patients that have switched from previous monotherapy with tiotropium.

Due to the lack of real-world evidence data on LABA/LAMA combinations in Greece, this non-interventional study (NIS) plans a prospective analysis of COPD patients who switch from tiotropium monotherapy (Spiriva® Handihaler®) to dual therapy with tiotropium bromide plus olodaterol (Spiolto® Respimat®) in the Greek private and public sector pulmonary offices and clinics, and specifically to assess the change in the quality of life in relation to health status variations in this target population of COPD patients.

The results from this study will be used to scientifically support the improvement on the impact of COPD on the patient's health and quality of life after three months of dual therapy with tiotropium bromide plus olodaterol (Spiolto® Respimat®), as well as to understand how switch of therapy in COPD patients who initiated this dual therapy after using Spiriva® Handihaler® is approached by the Greek healthcare providers.

8.2 STUDY OBJECTIVES

[figure not shown]
8.2.1 Primary objective

The primary objective of this non-interventional study (NIS) is to evaluate changes within 3 months in quality of life according to health status evaluated with the COPD Assessment Test (CAT) in COPD patients who have recently switched (within one week) from tiotropium monotherapy (Spiriva® Handihaler®) to dual therapy with tiotropium bromide plus olodaterol (Spiolto® Respimat®), in the Greek private and public sector pulmonary offices and clinics.

8.2.2 Secondary objectives

The secondary objectives are:

- To evaluate change in the proportion of patients with CAT ≥ 10 (representing impaired health status) within three months after the switch
- To evaluate changes in quality of life (QoL) according to EQ-5D-5L questionnaire within three-months after the switch
- To describe treatment adherence of COPD patients according to Simplified Medication Adherence Questionnaire (SMAQ)
- To describe patients' satisfaction and preference with inhaler devices according to Patient Satisfaction Questionnaire (PASAPQ) before and after the switch
- To describe patients' dyspnea status according to modified Medical Research Council (mMRC) scale within three months after the switch

9. RESEARCH METHODS

9.1 STUDY DESIGN

This is a non-interventional, 3-months prospective, two visits, single-cohort, multicenter, nationwide study in patients with stable COPD who have been using maintenance therapy with tiotropium monotherapy (Spiriva® Handihaler®) for at least 3 months before, and for whom, according to their treating physician, a recent switch (within one week) to dual therapy with tiotropium bromide plus olodaterol (Spiolto® Respimat®) have been required, in the Greek private and public sector pulmonary offices and clinics.

In all cases, the decision to switch the treatment strategy from Spiriva® Handihaler® to Spiolto® Respimat® will be previous and completely independent from the initiation of this non-interventional study. Additionally, the decision of the treating physician will be according to the daily clinical practice in the corresponding center.

The intended Health Care Professionals (HCPs) are office-based pulmonologists and practice physicians from Hospital pulmonary clinics, who are treating symptomatic COPD patients every day, being aware that most of their patients suffer from the physical restrictions induced by the disease *per se*.

Enrolment of patients will not be competitive. Each investigator will recruit up to 10 eligible patients in a consecutive manner from those who come to control visits and have been using tiotropium administered with Spiriva® Handihaler® for at least 3 months before the decision to switch to a combination therapy with tiotropium bromide plus olodaterol administered with Spiolto® Respimat® has been made. The enrolment period will last for a maximum of 9 months. All centers will stop recruitment once the total sample size of 1500 patients is achieved or, alternatively, at the end of the 9-months planned period of enrolment.

The study will collect data from two visits: baseline (within one week after the time of treatment switch) and approximately at 3 months (± 2 weeks, according to clinical practice) (see [Figure 1](#)). In case of premature discontinuation of Spiolto® Respimat® for any reason (including treatment discontinuation, withdrawal of patient willingness to participate, or unexpected patient problems to continue with the study), an additional unscheduled visit will be performed, if possible according to clinical practice. In this visit, the specific reason for discontinuation will be assessed and all the effectiveness and quality of life variables will be collected as planned for the regular final visit at 3 months (see [Table 1](#)).

Study results will be used to document the effectiveness of Spiolto® Respimat® in reducing the impact of COPD on patient's life. The biggest advantage of the current proposal is that the CAT is a well-known and widespread questionnaire, which is also included in the most recent GOLD guidelines ([1](#)). The CAT questionnaire also exhibits high reproducibility and is independent of various languages, as well ([17,18](#)).

Figure 1. Study scheme

[figure not shown]

Table 1. Visit flow chart and data collection parameters

Parameter	Visit 1 (baseline visit)	Visit 2 (3 months ± 2 weeks after baseline visit)¹	Unscheduled Visit (in case of premature discontinuation)
Informed Consent	X		
Inclusion / Exclusion Criteria	X		
	[REDACTED]	[REDACTED]	
COPD history and clinical characteristics	X	X	X
History of exacerbations in the year before	X		
History of exacerbations since baseline		X	X
Past COPD therapies (12 months before Visit 1)	X		
COPD related and other relevant concomitant medication	X	X	X
Respiratory comorbidities and allergies	X	X	X
Concomitant diseases / Comorbidities	X	X	X
	[REDACTED]	[REDACTED]	
COPD severity based on GOLD assessment ²	X	X	X
COPD Assessment Test (CAT)	X	X	X
EQ-5D-5L questionnaire	X	X	X
Simplified Medication Adherence Questionnaire (SMAQ)		X	X
Modified British Medical Research Council (mMRC) questionnaire	X	X	X
Abbreviated Patient Satisfaction Questionnaire (PASAPQ)		X	X
	[REDACTED]	[REDACTED]	[REDACTED]
Adverse Drug Reactions (serious and non-serious), fatal AEs, pregnancy	X	X	X
Rationale for Spiolto® Respimat® treatment discontinuation (if applicable)		X	X
Continuation or discontinuation of treatment with Spiolto® Respimat® after the study (yes/no)		X	X

¹ Premature discontinuation of the study will be considered for any reason including treatment discontinuation, withdrawal of patient willingness to participate, or unexpected patient problems to continue with the study.

² GOLD patient group (B, C or D) will be automatically calculated within the eCRF based on available exacerbation history, mMRC and CAT score.

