7. RATIONALE AND BACKGROUND

7.1 CURRENT COPD MANAGEMENT AND ASSESSMENT

Both pharmacologic and non-pharmacologic therapies in chronic obstructive pulmonary disease (COPD) should be guided, mainly, by disease severity, although the aim of any treatment is to improve patient symptoms, decrease exacerbations, and improve patient activity and quality of life (1).

The contribution of physical inactivity to disability in COPD and its impact on quality of life and health status is difficult to be distinguished from disease progression. However, it is clear that quality of life and health status is significantly lower in patients with COPD (2,3), evidencing that health status should be measured in addition to lung function in those patients in order to reach the management goals (2).

COPD prevents patients from carrying out daily activities due to exercise intolerance, which is often attributed to limited pulmonary function. Additionally, this inactivity may be related to avoidance of exertion as a result of fear of dyspnea. Furthermore, data from a study of 434 patients with COPD demonstrated that physical inactivity and fatigue is strongly correlated with health status and quality of life in its mental and physical components. Moreover, multivariate models adjusting for covariates, shown that increased fatigue and decreased physical and mental dimensions of health status were all associated to mortality in subjects with COPD, but not in non-COPD (4).

Treatment recommendations in GOLD report and NICE guidelines has based on symptoms and exacerbation history. GOLD assessment tool has divided COPD patients in four GOLD groups: A, B, C and D, which have had different recommendation for medication. Current international guidelines for COPD recommended long-acting inhaled bronchodilators, including β 2-agonists (LABA) and anti-muscarinic antagonists (LAMA) as first choice maintenance therapies in the treatment of COPD for GOLD B and C, D groups (1). LABA/LAMA fixed dose combination is recommended as a choice for group D (symptomatic frequent exacerbator) and may be considered as the initial choice for group B patients who have severe breathlessness.

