9.3 VARIABLES

9.3.1 List of variables

In this NIS, the following data collection about the changes after the switch from a maintenance therapy with tiotropium monotherapy (Spiriva® Handihaler®) to dual therapy with tiotropium bromide plus olodaterol (Spiolto® Respimat®) on quality of life and health status in 1500 COPD patients treated in the Greek private and public sector pulmonary offices and clinics will be collected in an e-CRF.

The data collection both at the baseline visit (immediately after the switch) and at 3 months visit (three months later) will consist of the following list of variables:

- ***COPD history and clinical characteristics at baseline and changes up to 3-months visit:***

Time since COPD diagnosis

COPD severity based on GOLD assessment (B, C, D group), if available

COPD: Chronic bronchitis/Emphysema/Other COPD

Smoking history and current status

Eosinophilia

FEV1/FVC ratio, if available

History of exacerbations in the year before baseline visit and between baseline and 3-months visit

- ***Respiratory comorbidities and allergies at baseline and changes up to 3-months visit:***

Pneumonia

Allergic rhinitis

Bronchiectasis

Lung diseases due to external agents

- **Comorbidities at baseline and changes up to 3-months visit:**

Diabetes mellitus

Osteoporosis

Cardiovascular diseases (including heart failure, atrial fibrillation and other arrhythmias)

Malignancies

Anxiety/depression

Insomnia

Pulmonary artery hypertension

Sleep apnea

Gastroesophageal reflux disease

Hemolytic anemia

Atopy

Sinusitis

Emphysema

- **Current and past COPD therapies** (in the period of one year before enrolment)

- **Relevant concomitant medications at baseline and changes up to 3-months visit:**

Use of concomitant inhalers

Other concomitant medications

- [REDACTED] [REDACTED])

- **COPD Assessment Test (CAT) (9)** (see [ANNEX 3](#))

The CAT is a patient-completed questionnaire assessing globally the impact of COPD (cough, sputum, dysnea, chest tightness) on health status. It is a unidimensional score based on 8 items each of them scaling from 0 to 5.

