## 8. VARIABLES

***COPD history and clinical characteristics at baseline and changes up to 3-months visit:***

- Months since COPD diagnosis, defined as: (Date at enrolment – Date of diagnosis)/30.5
- Gold group (A, B, C, D)

- COPD type (Chronic, bronchitis, Emphysema, Other)
- Number of exacerbations in the year before baseline (None, 1, 2, >2)
- Number of hospitalizations in the year before baseline (None, 1, 2, >2)
- Smoking Status (Never, Past, Current, Unknown)
- Packyears
- Presence of Eosinophilia (Yes, No)
- Months since PFTs performed, defined as: (Date of enrolment-Date of PFTS performed)/30.5
- FEV1/FVC % predicted ratio
- FEV1% predicted.

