### 8.3 Covariates

The following variables will be considered, among others, as covariates and will be examined in terms of their association with the primary outcome measure.

- Patient' s age at baseline (<65 years,  $\geq 65$  years)
- Sex (female, male)
- Obesity (i.e. BMI  $\geq 30$  kg/m^2) (yes, no)
- Smoking habits (current smoker, past smoker).
- Packyears
- Gold group (A, B, C and D).

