#### 11.2.1 Analysis of primary outcome.

11.2.1.1 Mean change in patients' quality of life (QoL) according to the total score of COPD Assessment Test (CAT) within three months after the switch from Spiriva® Handihaler® to Spiolto® Respimat®.

The primary estimand is defined as follows:

- A. Population: Is defined through inclusion/exclusion criteria of the study protocol to reflect the target population.
- B. Variable: Continuous variable response.

- C. Intercurrent Event (IE): Include death, drop-out due to any adverse event (AE) and treatment discontinuation. For patients experiencing an IE, the most extreme unfavourable value will be assigned (CAT score at 3 Months equals to 40).
- D. Population level summary: The change from Baseline of total CAT score within 3 Months.

Mixed model for repeated measurements (MMRM) assuming random missingness will be fitted. The dependent variable will be the CAT score at each visit. Visit, GOLD group, smoking habits, packyears, sex, age, and comorbidities appearing at a rate greater than 5% will be entered as covariates. Patients will be fitted at random and an unstructured covariance matrix will be used, allowing adjustment for correlations between study visits within the study patients. The Kenward- Roger degrees of freedom approximation will be used in the model (ddfm=kr).

Summaries of the estimated mean change from baseline of CAT score at 3 Months will be provided with 95% confidence interval. Model information will be provided as footnote under the corresponding table.

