**TABLE 17.9 SHIFT TABLE OF GOLD GROUP**

	Baseline		3 Months						Total	
	A	B	C	D	Missing					
	n	%	n	%	n	%	n	%	n	%
Gold group										
A										
B										
C										
D										
Missing										
Total										

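### The protocol limits the eCRF-calculated GOLD group to B, C or D, while eligibility admits group A and the SAP models and tabulates A to D

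*Protocol*

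**What the plan says.** Protocol:

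- Section 9.1, Table 1, footnote 2: "GOLD patient group (B, C or D) will be automatically calculated within the eCRF based on available exacerbation history, mMRC and CAT score". Table 1 schedules this assessment at Visit 1, Visit 2 and the unscheduled visit.
- Section 9.3.1 repeats the three levels: "COPD severity based on GOLD assessment (B, C, D group), if available".
- Section 7.1 describes the scheme with four: "GOLD assessment tool has divided COPD patients in four GOLD groups: A, B, C and D".
- Section 9.2.2 sets no minimum CAT, mMRC grade, exacerbation count or GOLD group in its four inclusion and nine exclusion criteria. Section 9.9 calls the entry criteria non-restrictive.

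SAP:

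- Section 8, variable list: "Gold group (A, B, C, D".
- Section 8.3, covariates: "Gold group (A, B, C and D".
- Table 17.9 has rows and columns for A, B, C, D and missing.
- Sections 11.2.1.1, 11.2.2.1, 11.2.2.2, 11.2.2.3 and 11.2.2.9 enter GOLD group as a covariate in the models for CAT, CAT ≥10, EQ VAS, the EQ-5D-5L dimensions and mMRC. None says whether this is the baseline or the visit-specific value.
- Section 11.2.1.1 says of the primary estimand's population: "Is defined through inclusion/exclusion criteria of the study protocol to reflect the target population".
- The readable part of section 5.1 does not list a move from three GOLD levels to four. Part of that section is redacted.

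**The concern.** The three-level list appears twice in the protocol, so it does not look like a single slip. A patient with few symptoms and few exacerbations can be enrolled, yet the stated calculation has no level for that patient. Group A may also arise at Month 3, when patients who improve are re-graded.

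At stake is a covariate in the primary model and four secondary analyses. CAT is one of the inputs to GOLD, so losing group A patients at baseline would not be random loss. It would remove patients with low values of the primary outcome, and those who remain would tend to fall by regression to the mean, a threat that protocol section 9.9 itself names. The modelled result would then no longer describe the population set by the eligibility criteria.

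**Working it through.** **Step 1. What can happen to a group A patient if footnote 2 is built as written.**

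| eCRF behaviour | Effect on models | Effect on Table 17.9 |
|---|---|---|
| Forced into B, C or D | Wrong covariate level | Wrong cell |
| Blank at baseline, record leaves the model | Selection on low baseline CAT; apparent improvement rises | Counted as missing |
| Blank at Month 3 only, visit-specific GOLD used | Loses low Month 3 scores; bias in the opposite direction | Shift to A not visible |

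SAP section 5.1 plans multiple imputation only above 25% missing. Above that level, imputation could draw only on observed B, C and D.

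**Step 2. Forced branch.** The primary model lists GOLD as a main effect with no visit interaction. A baseline value is constant within a patient, so with both visits complete it cancels from the Month 3 minus baseline contrast. Misclassification then hardly changes the CAT estimate.

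**Step 3. Blank branch, bias.** From protocol section 9.5: expected change 1.0 (written as −1.0, since lower CAT is better) and SD of change 9.0. Assumed, not in the documents: baseline CAT normal with mean μ and SD σ; group A is a share s of patients with CAT <10 (cut at 9.5 for whole-number scores); baseline to Month 3 correlation r, with equal SDs at both visits.

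- z = (9.5 − μ)/σ
- Group A share: A = s·Φ(z)
- Rise in baseline mean after removal: δ = s·σ·φ(z)/(1 − A)
- Mean change in those left: −1.0 − (1 − r)·δ
- Correlation implied by the SD of change: r = 1 − 81/(2σ²), which is 0.37 for σ = 8 and 0.17 for σ = 7

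Example with μ = 17, σ = 8, s = 0.6: z = −0.9375, Φ = 0.174, φ = 0.257. A = 0.6 × 0.174 = 10.5%. δ = 0.6 × 8 × 0.257/0.895 = 1.38. With r = 0.37 the change is −1.0 − 0.63 × 1.38 = −1.87. With r = 0.7 it is −1.0 − 0.3 × 1.38 = −1.41.

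| μ, σ, s | Group A | Change, r implied by SD 9.0 | Change, r = 0.7 |
|---|---|---|---|
| 20, 7, 0.3 | 2.0% | −1.23 | −1.08 |
| 17, 8, 0.6 | 10.5% | −1.87 | −1.41 |
| 14, 7, 0.9 | 23.4% | −3.21 | −1.80 |

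A separate simulation with scores rounded and held within 0 to 40 (means 14 to 22, SDs 6 to 8, r 0.5 to 0.7, s = 0.8) gave group A shares of 1.5% to 23% and changes from −1.07 to −2.35.

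**Step 4. Blank branch, precision.** The plan's own figure reproduces. The smallest n with t(0.975, n−1) × 9 × √[χ²(0.90, n−1)/(n−1)]/√n ≤ 0.5 is 1310, with coverage probability 0.901. Removing patients from 1310:

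| Lost | n left | Half-width t × 9/√n | Probability half-width ≤0.5 |
|---|---|---|---|
| 0% | 1310 | 0.488 | 0.90 |
| 2% | 1283 | 0.493 | 0.77 |
| 5% | 1244 | 0.501 | 0.48 |
| 10% | 1179 | 0.514 | 0.09 |
| 20% | 1048 | 0.546 | about 0 |

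**The case against.** The strongest reply is that the harm depends on an eCRF nobody outside the study can see. The SAP describes itself as the more technical document, lists A to D throughout and gives Table 17.9 an A row and an A column. Old protocol wording, with group A in fact recorded or re-derived, fits the text equally well. This stands, and the consequences must be stated conditionally. A reader might infer that the eCRF cannot return A and that such patients are being lost; the documents do not show this.

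Nor is it established that a blank GOLD value removes a patient. SAP section 10.2 refers to section 11.3.1 for detail on missing values, and that section is not readable. Protocol section 9.3.1 already allows GOLD to be unavailable. This stands too.

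Group A may also be uncommon at baseline, since physicians judged that a step-up was required. The CAT ≥10 outcome does not prove otherwise, because scores below 10 at Month 3 alone would give it content. Finally, the protocol's unadjusted mean change (section 9.7.1) and the observed-data summary in SAP Table 6.1.1 do not use GOLD, so a modelled estimate distorted in this way should visibly disagree with them. Both points limit the damage but leave the two category lists unreconciled.

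**Conclusion.** The inconsistency is confirmed: three GOLD levels in the protocol's calculation rule and variable list, four in its background and in the SAP, and no criterion that excludes the fourth. It is an internal inconsistency that should be fixed before analysis, not a demonstrated bias in the primary result.

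The size cannot be fixed from the documents. If baseline group A values are blank and those patients leave the adjusted model, the assumed inputs above add between 0.07 and about 2.2 CAT points of apparent improvement, against an expected change of 1.0 and a planned precision of ±0.5. A reader might take the upper end, a change of −3.2, as the likely result. It arises only at one corner of the assumptions: mean 14, SD 7, 90% of low scorers in group A and a correlation of 0.17. Raising the correlation to 0.7 gives −1.8. Against that, 0.7 with SD 7 implies an SD of change of 7 × √0.6 = 5.4, well below the protocol's 9.0, so neither column is the established one.

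If the value is forced into B to D and GOLD is a baseline covariate, the damage is mainly a wrong covariate and a wrong shift table.

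**What to change.** Use one category list, A, B, C and D, in Table 1 footnote 2, in protocol section 9.3.1 and in the eCRF calculation.

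If the eCRF is already live, add to the SAP:

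1. GOLD A to D is derived by program from the recorded CAT, mMRC and exacerbation history, with the cut-offs written out. Include the exacerbation look-back used at Visit 2, where Table 1 collects events only since baseline.
2. This derived value replaces the eCRF field in all models and in Table 17.9.
3. Baseline GOLD is the model covariate.
4. How a patient with a missing GOLD value is handled in the models.

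The cost is two wording changes and one derivation. All inputs are collected at both visits, so sites and patients carry no extra burden. With A to D in use, no patient is lost for this reason and the 1310 target is unaffected.

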9.2 SETTING

It is planned that data of approximately 1500 COPD patients from approximately 150 sites (around 148 office-based pulmonologists and 2 Hospital pulmonary clinics) throughout Greece will be collected. Each investigator will recruit up to 10 eligible patients in a consecutive manner who have been using tiotropium administered with Spiriva® Handihaler® for at least 3 months before the decision to switch to a combination therapy with tiotropium bromide plus olodaterol administered with Spiolto® Respimat® has been made, according to the daily clinical practice in the corresponding site.

9.2.1 Study sites

Patients will undergo visits 1 and 2 in private practice services and Hospital Pulmonary Clinics (centers) disposed by pulmonologists who will participate in the study.

9.2.2 Study population

Approximately 1500 patients with chronic obstructive pulmonary disease (COPD) who have recently switched (within one week) from Spiriva® Handihaler® to Spiolto® Respimat® according to the daily clinical practice in the corresponding site, are to be observed by approximately 148 pulmonologists in the setting of private practice and 2 Hospital Pulmonary Clinics all over Greece. Hospital Pulmonary Clinics will act as coordinating sites of the study.

The NIS will take place in Greece and sites in urban as well as rural areas will be included. The nationwide distribution of the participating pulmonologists as well as the number of patients enrolled are intended to ensure that the data collected are representative.

Possible contraindications are to be checked prior to switch treatment to Spiolto® Respimat®. See also the latest Summary of Product Characteristics of Spiolto® Respimat®.

Every physician should enroll the first consecutive patients presented for regular control visits immediately after the switch to Spiolto® Respimat®. As a consequence, enrolment of patients will not be competitive and each investigator will recruit up to 10 eligible patients in a consecutive manner up to the moment when the total sample size of 1500 patients is achieved or, alternatively, until the end of the 6-months planned period of enrolment.

The decision to treat will be taken independently of participation in this NIS, according to the daily clinical practice in the site, and will be made before participation is considered. Additionally, enrolled patients in the current NIS have to be already taking the new medication before the inclusion in the study is considered by the study investigators.

Inclusion criteria:

1. Female and male patients ≥ 40 years of age
2. Patients diagnosed with COPD who have been using tiotropium administered with Spiriva® Handihaler® for at least 3 months before a recent switch (within last week) to a combination therapy with tiotropium bromide plus olodaterol administered with Spiolto® Respimat® has been made
3. Written informed consent prior to participation

4. Patient should be able to read, comprehend and complete study questionnaires

Exclusion criteria:

1. Patients with contraindications according to Spiolto® Respimat® SmPC
2. Patients who have been treated with inhaled corticosteroids (ICS) as maintenance therapy* or with a LABA/LAMA combination (free or fixed dose) in the previous 6 weeks
**Note: patients with temporary corticosteroids (CS) use during acute exacerbations in the previous 6 weeks can enter the study*
3. Patients who have been treated with Spiriva® Respimat®, with other LAMA different than Spiriva®, or with a combination of Spiriva®+LABA/ICS in the previous 6 weeks
4. Patients diagnosed with asthma or with asthma COPD overlap syndrome (ACO)
5. Patients for whom availability at the enrolling site during the planned study period of approximately 3 months is not possible
6. Pregnancy and lactation
7. Patients currently listed for lung transplantation
8. Current participation in any clinical trial or any other non-interventional study of a drug or device.
9. Patients who initiated the treatment with tiotropium bromide plus olodaterol older than 7 days before their enrolment in the present study.

A subject screening log should be kept at the site, recording basic information (e.g. initials, gender, date of birth, reason for not enrolling the patient etc.) on all patients who were invited to participate in the study, with the information on the eligibility (or reasons for non-eligibility) and date of signed informed consent. In the case of refusal, reasons for refusal should be given. In addition, a log of all patients included into the study (i.e. having given informed consent) will be maintained in the study file at the study site.

